10.1.4. Data Protection

- Participants will be assigned a unique identifier. Any participant records or datasets that are transferred to the sponsor will contain the identifier only; participant names or any information that would make the participant identifiable will not be transferred.
- The participant must be informed that his/her personal study-related data will be used by the sponsor in accordance with local data protection law. The level of disclosure must also be explained to the participant.
- The participant must be informed that his/her medical records may be examined by Clinical Quality Assurance auditors or other authorized personnel appointed by the sponsor, by appropriate IRB/IEC members, and by inspectors from regulatory authorities.

10.1.5. Committees Structure

10.1.5.1. Data Safety Monitoring Board

An independent DSMB will be established to review unblinded safety data and summary reports, identify any safety issues and trends, and make recommendations to Allergan, including modification or ET of the study, if emerging data show unexpected and clinically significant AEs of treatment.

Details of the DSMB memberships, standard operational procedures for data monitoring/review, frequency of review, and other pertinent details will be provided in a separate DSMB Charter.

10.1.5.2. Hepatic Event Adjudication Committee

An Adjudication Charter will be established and will describe the process for the blinded surveillance, monitoring, and adjudication by the Clinical Adjudication Committee of events of post-treatment elevations of ALT and/or $AST = 3 \times ULN$ in the atogepant program. The purpose of this committee charter will be to provide a standardized process for the adjudication of data associated with these events in order to determine whether the elevation was related to atogepant.

10.1.6. Posting Clinical Study Data

Study information and tabular study results will be posted to the US National Institutes of Health website www.clinicaltrials.gov and other publicly accessible sites. Study data and information

may be published in non-promotional, peer-reviewed publications either by or on behalf of the sponsor. Clinical study reports, safety updates, and annual reports will be provided to the regulatory authorities as required.

10.1.7. Data Quality Assurance

- All participant data relating to the study will be recorded on printed or electronic CRFs unless transmitted to the sponsor or designee electronically (eg, laboratory data). The investigator is responsible for verifying that data entries are accurate and correct by physically or electronically signing the CRF.
- The investigator must maintain accurate documentation (source data) that supports the information entered in the CRF.
- The investigator must permit study-related monitoring, audits, IRB/IEC review, and regulatory agency inspections and provide direct access to source data documents.
- The sponsor or designee is responsible for the data management of this study including quality checking of the data.
- Study monitors will perform ongoing source data verification to confirm that data entered into the CRF by authorized site personnel are accurate, complete, and verifiable from source documents; that the safety and rights of participants are being protected; and that the study is being conducted in accordance with the currently approved protocol and any other study agreements, ICH GCP, and all applicable regulatory requirements.
- Records and documents, including signed ICFs, pertaining to the conduct of this study must be retained by the investigator as stated in the clinical trial agreement. No records may be destroyed during the retention period without the written approval of the sponsor. No records may be transferred to another location or party without written notification to the sponsor.
- For countries falling within the scope of the ICH guidelines, Allergan-specific essential documents should be retained until at least 2 years after the last approval of a marketing application in an ICH region and until there are no pending or contemplated marketing applications in an ICH region, or at least 2 years have elapsed since the formal discontinuation of clinical development of the study intervention. These documents should be retained for a longer period, however, if required by the applicable regulatory requirement(s) or if needed by Allergan.

In addition, for countries not falling within the scope of the ICH guidelines, local regulatory requirements should be followed regarding the retention of clinical study documentation.

10.1.8. Summary of Methods of Data Collection

An IWRS will be used to randomize participants and manage study intervention inventory. All visit data (ie, non-diary data) for this study will be collected by either the eTablet or, if conducted remotely (see Section 10.11, Appendix 11), utilizing a web-based portal (eg, questionnaires for PROs) or eCRFs via an electronic data capture system. Source documents will be used at the sites and may include a participant's medical record, hospital charts, clinic charts,

the investigator's participant study files, as well as the results of diagnostic tests such as laboratory tests, ECGs, etc. A centralized clinical laboratory will be used for the analysis of all blood and urine samples and for ECG assessments. Additional information on the collection and handling of samples is detailed in the laboratory manual.

Participants will use an eDiary daily to record the daily total duration of headache, headache characteristics, associated symptoms, the worst pain severity, and acute medication use both in the screening/baseline period and double-blind treatment period until Visit 7/ET. They also will record AIM-D, Activity level and Activity limitation, EQ-5D-5L in the eDiary during the double-blind treatment period and the safety follow-up period as indicated in the SoA, Section 1.3. Training for the eDiary will be provided for qualified participants during the Screening/Baseline Visit (Visit 1).

10.1.9. Source Documents

- Source documents provide evidence for the existence of the participant and substantiate the integrity of the data collected. Source documents are filed at the investigator's site.
- Data reported on the CRF or entered in the eCRF that are transcribed from source documents must be consistent with the source documents or the discrepancies must be explained. The investigator may need to request previous medical records or transfer records, depending on the study. Also, current medical records must be available.
- Definition of what constitutes source data is presented below:

Source documents may include a participant's medical records, hospital charts, clinic charts, the investigator's participant study files, as well as the results of diagnostic tests such as X-rays, laboratory tests, and ECGs. The investigator's copy of the CRFs serves as part of the investigator's record of a participant's study-related data.

The following information should be entered into the participant's medical record:

- Participant's name
- Participant's contact information
- The date that the participant entered the study, participant number, and study intervention kit numbers
- The study title and/or the protocol number of the study and the name of Allergan
- A statement that informed consent was obtained (including the date). A statement that written authorization (United States sites only), data protection consent (EU sites only), or other country and local participant privacy required documentation for this study has been obtained (including the date)
- Dates of all participant visits
- Participants medical history
- Information regarding participant's diagnosis of migraine headache
- All concurrent medications (List all prescription and non-prescription medications being taken at the time of enrollment. At each subsequent visit, changes to the list of medications should be recorded.)
- Occurrence and status of any AEs

- The date the participant exited the study, and a notation as to whether the participant completed the study or reason for discontinuation.
- The results of laboratory tests performed by the site (eg, results of urine pregnancy tests).
- Key study variables

Source documentation practices must follow Section 4.0 of ICH E6, GCP: Consolidated Guidance, and ALCOA-C (ie, records must be Attributable, Legible, Contemporaneous, Original Accurate and Complete).

10.1.10. Study and Site Closure

The sponsor or designee reserves the right to close the study site or terminate the study at any time for any reason at the sole discretion of the sponsor. Study sites will be closed upon study completion. A study site is considered closed when all required documents and study supplies have been collected and a study-site closure visit has been performed.

The investigator may initiate study-site closure at any time, provided there is reasonable cause and sufficient notice is given in advance of the intended termination.

Reasons for the early closure of a study site by the sponsor or investigator may include but are not limited to:

- Failure of the investigator to comply with the protocol, the requirements of the IRB/IEC or local health authorities, the sponsor's procedures, or GCP guidelines
- Inadequate recruitment of participants by the investigator
- Discontinuation of further study intervention development

If a study is prematurely terminated or suspended due to safety issues, the sponsor shall inform all investigators and the regulatory authorities of the termination or suspension and the reason(s) for the termination or suspension. The IRB/IEC is also to be informed promptly and provided the reason(s) for the termination or suspension by the sponsor or by the investigator, as specified by the applicable regulatory requirements. If a premature termination or suspension occurs, the sponsor shall remain responsible for providing resources to fulfill the protocol obligations and existing agreements for follow-up of participants enrolled in the study, and each investigator or authorized designee shall promptly inform enrolled participants, if applicable.

10.1.11. Publication Policy

- Allergan as the sponsor has proprietary interest in this study. Authorship and manuscript composition will reflect joint cooperation between multiple investigators and sites and Allergan personnel. Authorship will be established prior to the writing of the manuscript. As this study involves multiple centers, no individual publications will be allowed prior to completion of the final report of the multicenter study except as agreed with Allergan.
- The sponsor will comply with the requirements for publication of study results. In accordance with standard editorial and ethical practice, the sponsor will generally support publication of multicenter studies only in their entirety and not as individual site data.

- Authorship will be determined by mutual agreement and in line with International Committee of Medical Journal Editors authorship requirements.

10.1.12. Compliance with Protocol

The investigator is responsible for compliance with the protocol at the investigational site. A representative of the sponsor will make frequent contact with the investigator and his/her research staff and will conduct regular monitoring visits at the site to review participant and study intervention accountability records for compliance with the protocol. Protocol deviations will be discussed with the investigator upon identification. Significant protocol deviations will be reported to the IRB/IEC according to the IRB/IEC’s reporting requirements.

10.1.13. Participant Privacy

Written authorization (United States sites only), data protection consent (European sites only), and other documentation in accordance with the relevant country and local privacy requirements (where applicable) is to be obtained from each participant prior to enrollment into the study, and/or from the participant's legally authorized representative in accordance with the applicable privacy requirements (eg, HIPAA, European Union Data Protection Directive 95/46/EC [“EU Directive”]).

In accordance with HIPAA requirements, additional purposes of this study may include publishing of anonymous participant data from the study.

10.1.14. Coordinating Investigator

A signatory Coordinating Investigator will be designated prior to the writing of the clinical study report.

10.2. Appendix 2: Clinical Laboratory Tests

The tests detailed in [Table 10-1](#) below will be performed by the central laboratory. Blood and urine samples will be collected, processed, and stored according to the instructions provided by the laboratory.

Protocol-specific requirements for inclusion or exclusion of participants are detailed in [Section 5](#) of the protocol.

Additional tests may be performed at any time during the study as determined necessary by the investigator or required by local regulations.

Participants are not required to fast overnight before coming in for their appointments.

Investigators must document their review of each laboratory safety report.

Table 10-1 Protocol-required Laboratory Assessments

Category	Parameter
Chemistry	Sodium, potassium, chloride, bicarbonate, glucose, blood urea nitrogen, creatinine, total bilirubin, alkaline phosphatase, AST, ALT, lactate dehydrogenase, creatine kinase, total protein, serum albumin, calcium, phosphorus, uric acid, total cholesterol. The estimated glomerular filtration rate will be calculated by the central laboratory.

Hematology	Hemoglobin; hematocrit; red blood cell count; red blood cell indices (mean corpuscular volume, mean corpuscular hemoglobin, mean corpuscular hemoglobin concentration); white blood cell count, including differential (neutrophils, lymphocytes, monocytes, eosinophils, and basophils); platelet count
Urinalysis	Urine dipstick for specific gravity, pH, protein, glucose, ketones, bilirubin, and blood; microscopic exam including red blood cells/high-power field, white blood cells/high-power field, and casts/low-power field.
Coagulation	International normalized ratio
Serology	At Visit 1 only: anti-hepatitis A IgM antibody, hepatitis B surface antigen, anti-hepatitis C antibody, anti-hepatitis E IgM antibody
Urine Drug Screen	Screening for drugs of abuse (eg, marijuana, cocaine, phencyclidine, amphetamines, benzodiazepines, barbiturates, opiates) will be conducted using a urine drug screen at Visit 1. Urine drug screens positive for recreational (including cannabis regardless of legality) or illicit drugs or non-disclosed concomitant medications are not allowed to be repeated. All other positive urine drug screens may only be repeated with permission from the Sponsor. A negative result or an explanation of a positive result due to concomitant medication use (eg, benzodiazepines for insomnia) will be required for randomization.

10.3. Appendix 3: Adverse Events: Definitions and Procedures for Recording, Evaluating, Follow-up, and Reporting

Definition of AE

AE Definition

 An AE is any untoward medical occurrence in a patient or clinical study participant, temporally associated with the use of study intervention, whether or not considered related to the study intervention. An AE can therefore be any unfavorable and unintended sign (including an abnormal laboratory finding), symptom, or disease (new or exacerbated) temporally associated with the use of study intervention. 
AE of Special Interest
 
An adverse event of special interest (serious or nonserious) is one of scientific and medical concern specific to the sponsor’s study intervention or program, which warrants ongoing monitoring and rapid communication by the investigator to the sponsor. Such an event might warrant further investigation in order to characterize and understand it.
 
The following AESI(s) have been identified for the study intervention(s) in this protocol:
 
 Treatment-emergent suicidal ideations with intent, with or without a plan, (ie, Type 4 or 5 on the C-SSRS) or any suicidal behaviors. Treatment-emergent elevated ALT or AST laboratory value $\geq 3 \times$ ULN. Potential Hy’s law cases: elevated ALT or AST laboratory value that is $\geq 3 \times$ ULN and an elevated total bilirubin laboratory value that is $\geq 2 \times$ ULN and, at the same time, an alkaline phosphatase laboratory value that is $< 2 \times$ ULN.

Participants with any AESI(s) will be closely monitored. Selected nonserious and serious adverse events are of special interest and will require immediate reporting, recording, and follow-up.

Reporting requirements for ALT or AST elevations and potential Hy's law cases are outlined in Section 10.3.1. and 10.3.2. below. Responses to the C-SSRS that meet the above criterion will be captured in the eTablet and monitored by the sponsor. These AEs or events determined to be SAEs must be reported appropriately via the designated eCRFs and safety forms.

10.3.1. ALT or AST Elevations

A treatment-emergent ALT $\geq 3 \times$ ULN and/or AST $\geq 3 \times$ ULN is considered an AE of special interest.

Any participant with this laboratory result after study intervention was taken must have repeat testing within 48 to 72 hours to confirm the abnormality. For this repeat testing, the following laboratory tests must be drawn:

- hematology panel
- chemistry panels
- INR
- serum acetaminophen level
- urine drugs of abuse screen
- and blood alcohol level.

An extra blood serology sample must be collected and sent to the central laboratory for further diagnostic testing at a later date if needed. In addition, the investigator will perform a complete history and examination to evaluate the participant for possible liver disease.

All AEs of special interest must be reported to the sponsor within 24 hours of the time the investigator becomes aware of the event using the abnormal liver function reporting form and the AE eCRF. All new elements of history, physical examination, diagnostic testing results, and other relevant medical reports are to be reported for each AE of special interest.

If an ALT or AST $\geq 3 \times$ ULN is confirmed, close medical follow-up is required: For these participants, the following laboratory tests must be performed:

- anti-hepatitis A IgM
- hepatitis B surface antigen
- anti-hepatitis B core IgM
- hepatitis C antibody
- hepatitis C quantitative RNA by polymerase chain reaction
- anti-hepatitis E IgM
- anti-hepatitis E IgG

- Cytomegalovirus IgM antibody
- Epstein-Barr Virus IgM antibody.

The participant must be followed clinically and further medical evaluation (for other causes of acute hepatic injury) should be done per the judgment of the investigator and in conjunction with medical personnel at the sponsor site. In general, the chemistry panel should be repeated 1 to 2 times per week to follow the course of ALT/AST elevation.

Study intervention must be discontinued if any of the following criteria are met:

- ALT or AST $\geq 3 \times$ ULN and the participant is symptomatic with the appearance of fatigue, nausea, vomiting, right upper quadrant pain or tenderness, fever, rash, or eosinophilia ($>5\%$)
- ALT or AST $\geq 3 \times$ ULN and total bilirubin $> 2 \times$ ULN
- ALT or AST $\geq 3 \times$ ULN and INR > 1.5
- ALT or AST $\geq 5 \times$ ULN for more than 2 weeks
- ALT or AST $\geq 8 \times$ ULN

The participant may be rechallenged with study intervention only after consultation with the sponsor's Medical Monitor. For participants who are not rechallenged with study intervention, they should be discontinued from the study and complete an ET Visit (Visit 7/ET assessments) and 4-week Follow-up Visit. Participants should receive appropriate follow-up as per SoC.

The investigator must contact the sponsor's Medical Monitor to discuss all cases of confirmed ALT/AST elevation $\geq 3 \times$ ULN. All ALT/AST elevations must be followed until ALT and AST return to $< 1.5 \times$ ULN and there is full clinical resolution.

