7.1. Discontinuation of Study Intervention

A participant with a condition and/or a situation that, in the investigator's opinion, may put the participant at significant risk, may confound the study results, or may interfere significantly with the participant's participation in the study may be withdrawn from receiving study intervention. Discontinuation of study intervention also requires discontinuation from the study. Please see appropriate sections regarding final assessments to be completed for discontinuation from study.

The following conditions require participants to be withdrawn from study:

- Women who become pregnant will be withdrawn from the study and should refrain from taking further study intervention. The participant should return to the clinic for ET study procedures (Visit 7/ET), including the Safety Follow-up Visit (Visit 8) if study intervention was taken.
- Participants who reply with yes to Questions 4 or 5 in the suicidal ideation section indicating having suicidal ideation with intent (with or without plan) or yes to any question in the suicidal behavior section of the C-SSRS should receive appropriate follow-up as in routine clinical practice. The participant should return to the clinic for ET study procedures (Visit 7/ET), including the Safety Follow-up Visit (Visit 8) if study intervention was taken.
- Participants who meet any of the below study intervention discontinuation criteria related to abnormal liver function tests and are advised not to be rechallenged (see also Section 10.3.1):
 - ALT or AST $\geq 3 \times$ ULN and the participant is symptomatic with the appearance of fatigue nausea, vomiting, right upper quadrant pain or tenderness, fever, rash, or eosinophilia ($> 5\%$)
 - ALT or AST $\geq 3 \times$ ULN and total bilirubin $> 2 \times$ ULN
 - ALT or AST $\geq 3 \times$ ULN and INR > 1.5
 - ALT or AST $\geq 5 \times$ ULN for more than 2 weeks
 - ALT or AST $\geq 8 \times$ ULN

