7.3. Lost to Follow-up

A participant will be considered lost to follow-up if he or she repeatedly fails to return for scheduled visits and is unable to be contacted by the study site.

The following actions must be taken if a participant fails to return to the clinic for a required study visit:

- The site must attempt to contact the participant and reschedule the missed visit as soon as possible and counsel the participant on the importance of maintaining the assigned visit schedule and ascertain whether the participant wishes to and/or should continue in the study.
- Before a participant is deemed lost to follow-up, the investigator or designee must make every effort to regain contact with the participant (where possible, 3 telephone calls, and if necessary, a certified letter to the participant's last known mailing address or local equivalent methods). These contact attempts will be documented in the participant's source data.
- Should the participant continue to be unreachable, he/she will be considered to have withdrawn from the study.
- Discontinuation of specific sites or of the study as a whole are handled as part of Section 10.1 (Appendix 1).

8. Study Assessments and Procedures

- Study procedures and their timing are summarized in the SoA. Protocol waivers or exemptions are not allowed.
- Immediate safety concerns should be discussed with the sponsor immediately upon occurrence or awareness to determine if the participant should continue or discontinue study intervention.
- Adherence to the study design requirements, including those specified in the SoA, is essential and required for study conduct. All assessments will be conducted at the appropriate visits as outlined in Section 1.3, the SoA, and the timing of the visits should occur as close as possible to the day specified. At each visit, the participant will be asked if the participant changed the dose/regimen of any existing concomitant medications or initiated the use of any new concomitant medications since the last visit to ensure compliance with the protocol.

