10.3.2. Potential Hy's Law Cases

Sites must report every participant who meets the following potential Hy's law criteria if this occurs within the time the participant signs the ICF until 30 days after the last dose of study intervention:

- ALT or AST $\geq 3 \times$ ULN **AND**
- Total bilirubin $\geq 2 \times$ ULN **AND**
- Alkaline phosphatase $< 2 \times$ ULN

Study site personnel must report every participant who meets these criteria. Typically, all 3 analytes will be obtained from the same sample, but they may come from multiple samples taken within a 24-hour period. This requirement applies from the time the participant signs the ICF for the study until 30 days after the final protocol-defined study visit or the last known dose of study intervention (if the final visit does not occur). A laboratory alert for possible

Hy's law cases will be in place, to notify investigators and the sponsor immediately when the above criteria have been met. A possible Hy's law case must be faxed by the investigator to the sponsor on an abnormal liver function reporting form as soon as possible (within 24 hours of learning of the possible Hy's law case) to the fax number on the form or the SAE fax number, even if no AE has occurred. If the event is serious, please complete the SAE form. The eCRF for possible Hy's law cases must be completed within 7 calendar days. Every effort to determine the cause of the liver enzyme abnormalities must be made, and close monitoring should be initiated in conjunction with the medical monitor and medical safety physician and in accordance with the FDA Guidance for Industry, Drug-Induced Liver Injury: Premarketing Clinical Evaluation, July 2009. The participant should return to the study site and be evaluated as soon as possible, preferably within 48 hours from the time the investigator becomes aware of the abnormal results. This evaluation should include laboratory tests, detailed history, and physical assessment.

Events Meeting the AE Definition

- Any abnormal laboratory test results (hematology, clinical chemistry, or urinalysis) or other safety assessments (eg, ECGs, radiological scans, vital signs measurements), including those that worsen from baseline, considered clinically significant in the medical and scientific judgment of the investigator (ie, not related to progression of underlying disease); for example:
 - The test result is associated with accompanying symptoms, and/or

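### At total bilirubin of exactly 2 × ULN, an on-treatment potential Hy's law case can meet none of the five mandatory stopping criteria

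*Protocol*

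**What the plan says.** **Stopping rule.** Protocol 10.3.1 states "Study intervention must be discontinued if any of the following criteria are met" and lists five:

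1. ALT or AST ≥ 3 × ULN with listed symptoms or eosinophilia above 5%
2. ALT or AST ≥ 3 × ULN with total bilirubin > 2 × ULN
3. ALT or AST ≥ 3 × ULN with INR > 1.5
4. ALT or AST ≥ 5 × ULN for more than 2 weeks
5. ALT or AST ≥ 8 × ULN

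Section 7.1 repeats the list with the same strict bilirubin operator. After a stop, 10.3.1 says: "The participant may be rechallenged with study intervention only after consultation with" the sponsor's Medical Monitor.

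**Potential Hy's law.** Section 10.3.2 says "Sites must report every participant who meets the following potential Hy's law criteria": ALT or AST ≥ 3 × ULN, total bilirubin ≥ 2 × ULN and alkaline phosphatase < 2 × ULN. The definition of adverse events of special interest in Appendix 3 also uses the inclusive bilirubin limit, as do SAP 10.2.5, SAP 10.3 and SAP Table 16. Section 10.3.2 requires reporting, monitoring and evaluation of these cases. It does not itself require study drug to stop.

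**The concern.** The same appendix classes bilirubin of exactly 2 × ULN as part of a potential Hy's law case but leaves that value out of the stopping rule. One reportable value higher, the drug must stop and can restart only after Medical Monitor consultation. At the boundary, whether to continue is decided case by case. The protocol gives no reason for the difference, and every ALT/AST limit in the stop list is inclusive.

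What is at stake is a participant-safety decision threshold for on-treatment cases. The Hy's law reporting window also covers time before and after dosing, when there is no drug to stop.

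**Working it through.** The plan states no figure to reproduce, so the check is one of logic.

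**Inputs.** The five stops come from Protocol 10.3.1 (and 7.1). The three Hy's law conditions come from 10.3.2. In multiples of ULN, except for INR, they are:

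- Hy's law: ALT/AST ≥ 3, bilirubin ≥ 2 and ALP < 2.
- Stop: (ALT/AST ≥ 3 and symptoms or eosinophilia) or (ALT/AST ≥ 3 and bilirubin > 2) or (ALT/AST ≥ 3 and INR > 1.5) or (ALT/AST ≥ 5 for more than 2 weeks) or (ALT/AST ≥ 8).

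**One example.** Take an asymptomatic participant with ALT 4, bilirubin 2.0, ALP 0.9 and INR 1.0. All three Hy's law conditions are met, and 0 of the 5 stops.

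**Enumeration.** The test values sit at and around each threshold:

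| Item | Values | Levels |
|---|---|---|
| ALT/AST with duration | 3 and 4.9 (duration not applicable); 5, 7.9 and 8 (each with and without more than 2 weeks at ≥ 5) | 2 + 3 × 2 = 8 |
| Bilirubin | 1.9, 2.0, 2.1 | 3 |
| INR | 1.0, 1.5, 1.6 | 3 |
| Symptoms or eosinophilia | no, yes | 2 |
| ALP | 1.0, 1.9, 2.0 | 3 |

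- All combinations: 8 × 3 × 3 × 2 × 3 = 432.
- Potential Hy's law (bilirubin 2.0 or 2.1; ALP 1.0 or 1.9): 8 × 2 × 3 × 2 × 2 = 192.
- Hy's law with no stop as written: 4 ALT/AST states (3, 4.9, and 5 or 7.9 not beyond 2 weeks) × 2 INR values (1.0, 1.5) × 2 ALP values = 16. All 16 have bilirubin 2.0 and no symptoms. None occurs at bilirubin 2.1 or at ALT/AST 8.
- Hy's law with no stop if the criterion reads ≥ 2 × ULN: 0.
- Extra stops created by that change: 4 × 2 × 3 ALP values = 24. These are the 16 above plus 4 × 2 = 8 with ALP 2.0, which are not potential Hy's law.

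The counts depend on the test values chosen and are not expected numbers of participants. The result that does not depend on the grid is that every uncovered case lies at equality.

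**Can equality be reported?** SAP Table 19 gives total bilirubin to one decimal in mg/dL. The sample narrative layout in SAP Table 20 shows an upper limit of 1.1 mg/dL, and 2 × 1.1 = 2.2 mg/dL is a reportable value. That table only illustrates a format; this trial's central laboratory range is not given.

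**The case against.** The strongest reply is that the two rules do different jobs. Section 10.3.2 is a reporting trigger and 10.3.1 a drug stop. No text says they must match, and the stop has no alkaline phosphatase condition. A reporting trigger slightly wider than a stop is coherent. That is fair as far as it goes, but the protocol gives no reason to leave out this one value. The SAP change log also records that the sponsor moved its SAP Hy's law definition from > to ≥. The log does not name the analyte, so this shows only that the operator was thought worth revising.

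The second reply is that the case is already managed, and this stands:

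- A laboratory alert notifies the investigator and sponsor at once, and the case is reported within 24 hours.
- Section 10.3.2 says "close monitoring should be initiated in conjunction with the medical monitor and medical safety physician", with evaluation at the site preferably within 48 hours.
- Repeat chemistry and INR are due within 48 to 72 hours. Any rise above 2 × ULN with ALT/AST still ≥ 3 × ULN then triggers the stop.
- The Medical Monitor must be contacted once ALT/AST ≥ 3 × ULN is confirmed.
- Section 8 calls for immediate discussion with the sponsor "to determine if the participant should continue or discontinue study intervention".
- Under 7.1 a participant judged to be at significant risk "may be withdrawn from receiving study intervention".

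The decision is therefore not left to the investigator alone. These routes limit the consequence but do not supply the automatic stop.

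The third reply is rarity and timing. Entry requires ALT, AST and bilirubin no higher than 1 × ULN (Gilbert's disease excepted for bilirubin), and Section 2.2 reports no hepatic signal to date. The final SAP, dated 21 August 2022, refers to Asia/Pacific enrolment in the past tense, so there may be little occasion left to amend. Both points support a low grading. Neither makes the rule consistent.

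**Conclusion.** The concern holds and is minor. The uncovered case needs all of the following on treatment:

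- bilirubin exactly 2 × ULN and alkaline phosphatase < 2 × ULN
- ALT/AST ≥ 3 and < 8 × ULN, and not ≥ 5 × ULN for more than 2 weeks
- INR ≤ 1.5
- no listed symptoms and no eosinophilia above 5%

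Above that bilirubin value the stop always applies. No frequency is claimed, because the laboratory's ULN and reporting resolution are not in the documents. The conclusion rests only on reading the operators as written. Efficacy analyses, power and type I error are untouched.

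**What to change.** Change > 2 × ULN to ≥ 2 × ULN in the bilirubin stopping criterion in Protocol 7.1 and 10.3.1. Leave the Hy's law definition as it is.

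The edit is one symbol in two places, with no new tests and no SAP change. The clinical cost is an occasional extra stop at the boundary, including some participants with alkaline phosphatase ≥ 2 × ULN who are not potential Hy's law cases. Rechallenge after Medical Monitor consultation makes it reversible.

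Under 10.1.1 an amendment needs IRB/IEC approval, and regulatory approval where national law requires it. The change should therefore ride with the next amendment rather than prompt one. If dosing has ended, it should be carried into any later protocol that reuses this text.
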